1. KEY ROLES

Protocol Committee- Responsible for developing a detailed study protocol, provides oversight on study progress and acts to correct deficiencies in the conduct of the study. This committee also drafts the main publications related to the study.

Steering Committee- The Science Committee of the METRC Consortium will review the composition of the protocol committee and provide scientific review of the study protocol, with the purpose of presenting the protocol to the Consortium Steering Committee for approval. Additionally, the study will have a Steering Committee comprised of the study investigators, an orthopaedic and general surgery investigator from each participating center, 2-3 experts on clot prevention, and the patient and consumer stakeholders who comprise our Stakeholder Advisory Committee.

METRC Coordinating Center- Responsible for maintaining all study documentation, developing and maintaining the master IRB application and consent, circulating any changes to study documents including protocols, case report forms, and IRB materials to each participating center, providing daily oversight and management of study implementation, providing payment to sites for patients enrolled, performing site monitoring, data quality control and analysis of study results.

Clinical Sites- Responsible for the conduct of clinical studies including patient enrollment, performing study procedures, data collection and conducting study follow-up visits.

Clinical Outcome Adjudication Committee (COAC)- This committee will be responsible for developing the timely medical review and adjudication of trial-specific endpoints utilizing trial-specific definitions; engages other reviewers as needed and in accordance with the COAC Policy; and reports adjudication results to the trial-specific Protocol Committee.

Publication Committee- Responsible for reviewing manuscripts prior to journal submission and reviewing presentations prior to presentation; for mediating and settling disputes and conflicts among study investigators over publication or presentation priorities, authorship, and any other issues related to publications or presentations; for preparing and maintaining a list of concepts for publications and preparing and maintaining a list of approved METRC publications, which shows the status of each manuscript from initiation through publication.

DSMB- Independent Data and Safety Monitoring Board (DSMB) convened for this project, responsible for monitoring the accumulated interim data as the trial progresses to ensure patient safety and to review efficacy, evaluate recruitment, and assess overall data quality.

Medical Monitor- Responsible for providing medical guidance and overseeing patient safety for the study. The MM participates in determining the course of action necessary to meet safety

The PREVENT CLOT study protocol is the confidential intellectual property of the PREVENT CLOT Principal Investigators, Steering Committee, and the University of Maryland Baltimore and METRC and cannot be used in any form without the expressed permission of the Principal Investigators.

goals and objectives. This is achieved through the review of safety reports; resolving safety issues; and interacting with Principal Investigators.

2. BACKGROUND INFORMATION AND SCIENTIFIC RATIONALE

2.1 Background Information

Importance of Blood Clots and Blood Clot Prevention Medicines. Preventing venous thromboembolism (VTE) in the legs or lungs is a major unsolved problem in modern medicine. Each year, in the United States alone, blood clots are estimated to affect 300,000 – 600,000 patients.¹ These events may have important consequences for patients. VTE can include both deep venous thrombosis (DVT) and pulmonary embolism (PE). Even minor blood clots require a minimum of 6 months of medication, often with frequent blood tests, and increased risk of medication-related bleeding. At the most severe end, PEs are thought to account for 60,000–100,000 deaths per year in the United States.²

Patients who sustain trauma are well known to be at an increased risk for blood clots throughout their body, including fatal PE's.³ There are 6 million fractures treated each year in the United States alone and 2.3 million patients are admitted each year after trauma.⁴⁻⁶ Hip and femur fractures specifically are among the most common fractures and are associated with a particularly high risk of blood clots.^{7,8} Current guidelines indicate that most orthopaedic trauma patients should be given medication to reduce the risk of blood clots.^{9,10} Despite the common nature of these injuries and the potential devastating impact that blood clots can have on patients' lives, we currently do not know the best prophylactic regimen for these patients.

The ideal clot prevention medication for orthopaedic trauma patients would prevent death from PE and other consequences of blood clots while also limiting complications from the medication, such as bleeding from surgical wounds and other sources.¹¹ A blood clot resulting in death is obviously a devastating outcome for a patient and their family; however, other complications from clot prevention medications are not insignificant and may require surgery and have a major impact on the lives of patients, including, permanent disability in some cases.^{12,13} Even under ideal conditions the medications used to reduce clots cannot completely eliminate the chance of blood clots and in some instances may lead to death themselves.¹²⁻¹⁴

Low molecular weight heparins (LMWH) are medications that have been utilized to lower the rates of proximal deep venous thrombosis in trauma patients since the 1990's and are currently the preferred agents across many guidelines, including those from the American College of Chest Physicians and the Eastern Association for the Surgery of Trauma.^{9,10} The case for the use of LMWH in this trial is relatively straight forward as it is the current treatment recommended by these guidelines and is commonly used in most north American trauma centers. While these guidelines are well intentioned, they are based on limited evidence regarding fracture patients, and do not incorporate patient preferences. There is good evidence that LMWH's are effective at limiting DVT, particularly asymptomatic DVT found on screening studies as a part of a research protocol.^{3,15,16} However feedback from patients indicates that they are more concerned with PE's

A Randomized Pragmatic Trial Comparing the Complications and Safety of Blood Clot Prevention Medicines Used in Orthopaedic Trauma Patients Version 11.0 6/1/2021 11

The PREVENT CLOT study protocol is the confidential intellectual property of the PREVENT CLOT Principal Investigators, Steering Committee, and the University of Maryland Baltimore and METRC and cannot be used in any form without the expressed permission of the Principal Investigators.

that might cause death or clot prevention medication-related complications that require surgical treatment, rather than blood clots in the leg that are often asymptomatic or of minimal clinical consequence. This was confirmed by our own pilot research (conducted under a separate IRB). We interviewed 232 orthopaedic trauma patients and found that patients value the prevention of death and avoidance of surgical complications much more than other issues related to clot prevention medications.¹⁷

Despite the widespread use of LMWH to reduce PE after orthopaedic trauma, a recent Cochrane review actually showed limited evidence that LMWH affects the rate of PE or mortality in trauma patients,³ and there is concern that there is potential for higher rates of bleeding into critical organs and surgical wounds associated with LMWH compared to other clot prevention medications in non-trauma related orthopaedic surgery.¹⁸⁻²⁰ This has led many to wonder if there is another alternative to clot prevention than LMWH for trauma patients.

Aspirin is another commonly used clot prevention medication, which may have a similar efficacy at preventing both PE and death in lower extremity injuries.²¹ For both hip fracture and lower extremity arthroplasty surgery, substantial reductions in surgical wound hematomas have been noted with aspirin.²² In addition, after lower extremity arthroplasty, LMWH has been associated with higher all-cause mortality as compared to the use of aspirin.¹² Although there are certainly strong advocates for the use of aspirin in orthopaedic trauma patients and some solid studies in arthroplasty supporting its use,^{21,23-25} the efficacy of ASA has not been characterized relative to LMWH in this population yet.

No Data for Guidelines: A recent study on this topic by the Orthopaedic Trauma Association Evidence Based Quality Value and Safety Committee highlighted a knowledge gap surrounding clot prevention in orthopaedic trauma patients and concluded that there is “wide variability in practice patterns, poor scientific support for various therapeutic regimens” and guidelines are needed to “improve patient care.”²⁶ As demonstrated by this study, there is a clear need for guidelines on clot prevention in trauma patients,²⁶ but there are no large high quality trials upon which to base these guidelines, as described by the Cochrane review on this topic.³ Most of the existing guidelines make recommendations that are based on either arthroplasty patients (who are a poor surrogate for trauma patients), or an older subset of hip fracture patients, limiting the applicability to the vast majority of patients who fundamentally differ from either of these groups. Unfortunately, this knowledge gap leaves clinicians and patients to make decisions about which VTE prophylaxis to use in this large patient population without adequate data to guide them.

2.2 Rationale

The best medication to reduce the risk of fatal PE for orthopaedic trauma patients who are admitted to a hospital after trauma each year in the United States is still unknown, creating decisional uncertainty for both patients and clinicians.²⁶ Recent meta-analysis on medications to prevent blood clots after major lower extremity surgery included no studies involving high energy trauma and only two small studies on hip fractures, concluding that “the rarity of

The PREVENT CLOT study protocol is the confidential intellectual property of the PREVENT CLOT Principal Investigators, Steering Committee, and the University of Maryland Baltimore and METRC and cannot be used in any form without the expressed permission of the Principal Investigators.

pulmonary embolism made meaningful comparisons between aspirin and anticoagulation impossible ...”²² The rarity of PE requires a large trial to answer this question and none exist to date. Similarly, a recent Cochrane review on this topic in trauma patients did not address the use of aspirin for clot prevention presumably due to a complete lack of data on the topic.³

There is little data on how commonly used medications like LMWH perform in trauma patients relative to enteral aspirin, likely because of the large patient sample size needed to address this issue. Moreover, the currently limited research in this topic has focused more on clinically insignificant DVTs, and have not been powered to address the outcomes most important to patients and clinicians, including bleeding complications and fatal PE.^{3,22}

In addition to the lack of guidelines to support clinical decision making, there is a lack of evidence on how the choice of chemoprophylaxis following orthopaedic trauma affects patient satisfaction. Factors that are important to patients such as the need for the medicine to be injected or the out of pocket costs have been almost totally ignored to date.^{3,22,26,27}

To address these critical gaps in the evidence we have designed a large, pragmatic, multicenter randomized clinical trial. This trial will provide definitive evidence for decision makers on whether aspirin is as effective as LMWH at preventing death and symptomatic PE, while potentially resulting in significantly fewer medication associated complications. The study fills several large and critical knowledge gaps of great interest to patients and clinicians and has great potential to improve the quality of evidence available for patients and other stakeholders to make informed decisions.

2.3 Potential Risks and Benefits

2.3.1 Potential Risks The risks associated with participation in this study are primarily the risks that are associated with each of the study drugs.

Patients randomized to the LMWH arm would have no drug-related risk over and above the risk they would experience as standard of care. These risks include bruising or infection at the site of injection and allergic reaction, ranging from hives and itching to difficulty breathing or throat swelling. Some participants may experience Heparin Induced Thrombocytopenia, which results in a reduced number of platelets and hypercoagulability. Risks associated with the LMWH arm also include bleeding complications, which could require transfusion or operation, and kidney damage.

Patients randomized to the aspirin arm would have no drug-related risk over and above the risk they would experience as using aspirin for blood clot prevention. These risks include the potential to experience the risks associated with aspirin, including possible risk of inflammation or ulceration of the stomach, allergic reaction (ranging from hives and itching to difficulty breathing or throat swelling), ringing of the ears, and worsening asthma. Additionally, some patients have increased risk of bleeding and of kidney damage.

The PREVENT CLOT study protocol is the confidential intellectual property of the PREVENT CLOT Principal Investigators, Steering Committee, and the University of Maryland Baltimore and METRC and cannot be used in any form without the expressed permission of the Principal Investigators.

There is potential that patients in the aspirin arm will be at lower or higher risk relative to the patients in the LMWH arm just as there is a risk for patients in the LMWH arm to have better or worse outcomes than those in the aspirin arm. The trial is designed to assess this potential difference in risk.

A DSMB for the study will closely monitor event reporting, and should differential risks or benefits be identified, will consider stopping the study.

In this study, as with many others, there is a potential risk of breach of confidentiality, although the study team will make all reasonable efforts to mitigate this risk.

2.3.2 Potential Benefits It is not clear that one drug treatment will provide any benefit over another. Patient participants will receive \$20 as compensation for time and effort returning for the 3-month study visit.

3. STUDY OBJECTIVES & OUTCOMES

3.1 Primary Objective:

We aim to make the following comparisons between aspirin and the LMWH:

Specific Aim 1: Compare the proportion of patients who die after orthopaedic trauma treated with LMWH compared to those treated with aspirin. (Hypothesis 1: Aspirin will be non-inferior to LMWH.)

Specific Aim 2: Compare the proportion of patients who sustain non-fatal PE or deep vein thrombosis (DVT) after orthopaedic trauma treated with LMWH compared to those treated with aspirin. (Hypothesis 2: Aspirin will be non-inferior to LMWH.)

Specific Aim 3: Compare the proportion of patients who sustain a bleeding event, a wound complication, or deep surgical site infection (SSI) after orthopaedic trauma patients treated with LMWH compared to those treated with aspirin. (Hypothesis 3: The rate of complications will be superior (i.e., lower) in the aspirin group compared to LMWH.)

3.2 Secondary Objectives:

We will pursue the following secondary aims:

Secondary Aim #1: Assess satisfaction with care in orthopaedic trauma patients treated with injectable LMWH compared to those treated with aspirin. (Hypothesis 4: Satisfaction will be superior in the aspirin group.)

Secondary Aim #2: Estimate out of pocket patient costs in orthopaedic trauma patients treated with injectable LMWH compared to those treated with aspirin. (Hypothesis 5: Out of pocket costs will be lower in the aspirin group.)

3.3 Study Outcomes

The PREVENT CLOT study protocol is the confidential intellectual property of the PREVENT CLOT Principal Investigators, Steering Committee, and the University of Maryland Baltimore and METRC and cannot be used in any form without the expressed permission of the Principal Investigators.

To meet study objectives, the following clinical outcomes will be assessed:

3.3.1 Primary Outcome

All-Cause Mortality

The primary outcome for this study is all-cause mortality by 90 days post-randomization. The primary study outcome was changed from PE-related death to all-cause mortality during the course of the trial. At the recommendation of an external peer reviewer for the protocol manuscript, the trial's steering committee determined that it was unfeasible to adjudicate death due to pulmonary embolism (PE) with reasonable certainty. Misclassification of the primary outcome of PE-related death would bias the results to non-inferiority. As such, the trial's steering committee decided to change the primary outcome from PE-related death to all-cause mortality. All-cause mortality was viewed as more important than PE-related death by our patient stakeholder and protocol committees and had greater scientific reliability. The DSMB was not involved in these decisions due to their knowledge of treatment effect from interim analyses. The decision of the trial's steering committee to change the primary outcome and non-inferiority margin was supported by the protocol committee, patient stakeholder committee, and sponsor.

3.3.2 Secondary Efficacy Outcomes

Cause-Specific Death

Cause-specific death will remain as a secondary outcome. Cause of death will be recorded in addition to an assignment of certainty of the attribution. The study's 3-person Clinical Outcome Adjudication Committee (COAC) is composed of experts not otherwise involved in any other aspect of the study. The committee is blinded to treatment arm and receives these data with the goal of classifying the death into 1 of 5 categories: a) *Certainly PE* (e.g., an autopsy or operative note indicates cause of death), b) *More likely to be caused by PE than something else* (e.g., clinical information available indicating likely cause of death, but no autopsy or corroborating data available), c) *Equally likely to be caused by PE or something else* (e.g., patient did not die in a clinical setting, and only data available to support assignment of causality is based on the report on non-clinical family or friends), d) *More likely to be a cause other than PE* (e.g., the clinical course was highly suggestive that the cause of death was not PE), and e) *Certainly not due to PE* (e.g., the cause of death was not related to a PE). There must be agreement among at least 2 of the 3 committee members, with no more than 1 level of disagreement among members, for the cause of death category determination to be finalized. We will report cause-specific death as: i) category a or b; ii) category a, b, or c; iii) category d or e.

Non-Fatal Pulmonary Embolism

Non-fatal PE is a key secondary outcome. The local site investigators categorize PE events, which are adjudicated centrally as one of four levels: *Massive* and *submassive* PE events are

The PREVENT CLOT study protocol is the confidential intellectual property of the PREVENT CLOT Principal Investigators, Steering Committee, and the University of Maryland Baltimore and METRC and cannot be used in any form without the expressed permission of the Principal Investigators.

defined based on the American Heart Association recommendations²⁴; *Other clinically significant* PE events are determined when a diagnostic test was performed due to symptoms or signs concerning for PE, but the symptoms or signs do not meet the *massive* or *submassive* criteria; *Other clinically insignificant* PE events include PEs found incidentally, or as part of a test performed for screening, or for another reason that does not meet the definition of “clinically significant.” Additionally, PE events are sub-classified as being segmental or non-segmental. Similar to the adjudication of the cause of death, the categorization of PE requires two-thirds consensus from the COAC. We report non-fatal PE as: i) any level; ii) sub-classified as massive, sub-massive, clinically significant, clinically non-significant; and iii) sub-classified as segmental, non-segmental.

Deep Vein Thrombosis (DVT)

DVT can be either symptomatic or asymptomatic and require a confirmed imaging diagnosis. We will report all confirmed symptomatic DVT events, and subclassified by proximal DVT and distal DVT.

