10.5 Analysis Plan

10.5.1 Intention to Treat Analysis

Patients will be followed for 3 months post-randomization. The primary statistical analysis will follow the intention-to-treat paradigm, which means all patients will be analyzed according to the treatment group to which they were randomized. The primary estimand (difference in all-cause mortality between treatment groups) will be estimated using treatment-specific Kaplan-Meier estimators. The other intention-to-treat estimands will be estimated using treatment-specific cumulative incidence function estimators. Formal definitions of the estimands are provided in the *Statistical Analysis Plan*.

We will test the primary outcome for non-inferiority using the upper bound of a two-sided 96.2% confidence interval compared to the pre-specified non-inferiority margin of 0.75%. If non-inferiority is established at our pre-specified non-inferiority margin, we will test for superiority.

Two-sided 95% confidence intervals will also be presented for all other outcomes, but null-hypothesis significance tests will not be performed.

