• Documented prescribed prophylaxis and duration • Out of pocket costs • Satisfaction • Prescribed medications • Any other treatment for PE/VTE event • Re-hospitalizations related to PE/VTE event—review medical records • Imaging studies • Post discharge surgeries ○ Planned elective surgeries • Complications (type, severity, treatment) ○ Fatal bleed ○ GI bleed ○ $\geq 2\text{g/dL}$ drop in hemoglobin ○ reoperation for hematoma evacuation ○ other clinical significant bleeding ○ infectious complication ○ VTE ○ DVT (blood clot in arms/legs) ○ Pulmonary Embolism ○ Imaging studies for bleeding or VTE			

The PREVENT CLOT study protocol is the confidential intellectual property of the PREVENT CLOT Principal Investigators, Steering Committee, and the University of Maryland Baltimore and METRC and cannot be used in any form without the expressed permission of the Principal Investigators.

	Baseline	Baseline – 3 months	3 month
Assessment			

 ○ Surgical wound infection ○ Surgical wound hematoma ○ Abnormal postoperative bleeding ○ Any complications secondary to treatment since hospitalization 			
CRF08: Patient Follow-up			X

 • Hospitalizations r/t PE/VTE outside the study center • TSQM: Treatment Satisfaction Questionnaire for Medication 			
CRF09: Diagnosis of Infection	X	X	X

 • CDC Criteria • Culture Data • Lab Data • Imaging Studies • Wound Characteristics • Time to Wound Closure • Type of Soft Tissue Coverage • Limb Complications (type, severity, treatment) 			
CRF10: SAE	X	X	X
Unanticipated events possible related to exposure to study medications (angioedema, agranulocytosis, hepatic injury, Stevens Johnson syndrome), other events that are serious and either related or possibly related to the study, other events that are unexpected and serious and either related or possibly related to the study beyond the expected complications.			

The PREVENT CLOT study protocol is the confidential intellectual property of the PREVENT CLOT Principal Investigators, Steering Committee, and the University of Maryland Baltimore and METRC and cannot be used in any form without the expressed permission of the Principal Investigators.

Summary of Protocol Amendments

The following summarizes the major actions taken regarding the master protocol.

Date	Action
3/1/2017	Johns Hopkins Bloomberg School of Public Health IRB (JHBSPH) granted initial approval.

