7.3.3 Secondary Efficacy Estimands

Cause-Specific Mortality

2. Difference (aspirin minus LMWH) in the probability of being *observed* to die due to PE (using categories a and b from Section 7.2) by 90 days for eligible patients under assigned treatment, in a world without loss-to-followup;
3. Difference (aspirin minus LMWH) in the probability of being *observed* to die due to PE (using categories a, b and c from Section 7.2) by 90 days for eligible patients under assigned treatment, in a world without loss-to-followup;
4. Difference (aspirin minus LMWH) in the probability of being *observed* to die due to non-PE (must be in category d or e from Section 7.2) causes of death (e.g., myocardial infarction, stroke, bleeding) by 90 days for eligible patients under assigned treatment, in a world without loss-to-followup;

Non-Fatal Pulmonary Embolism

5. Difference (aspirin minus LMWH) in the probability of being *observed* to have a non-fatal PE by 90 days for eligible patients under assigned treatment, in a world without loss-to-followup, where non-fatal PE will be categorized in (i) aggregated, (ii) sub-classified as massive, sub-massive, clinically significant, clinically non-significant and (iii) sub-classified as segmental, non-segmental;

Deep Vein Thrombosis

6. Difference (aspirin minus LMWH) in the probability of being *observed* to have a DVT by 90 days for eligible patients under assigned treatment, in a world without loss-to-followup; where DVT will be categorized as (i) any, (ii) proximal, and (iii) distal.

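### The protocol commits to reporting symptomatic DVT, but SAP Estimand 6 counts DVT by location with no symptom condition, so no estimand yields the promised result

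*Combined protocol and SAP*

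**What the plan says.** The protocol text is Version 11.0; the SAP is dated January 21, 2021. Both are current.

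- **Protocol 3.3.2, definition:** "DVT can be either symptomatic or asymptomatic and require a confirmed imaging diagnosis".
- **Protocol 3.3.2, reporting, in the next sentence:** "We will report all confirmed symptomatic DVT events, and subclassified by proximal DVT and distal DVT".
- **Protocol 3.1, Specific Aim 2:** "Compare the proportion of patients who sustain non-fatal PE or deep vein thrombosis (DVT) after orthopaedic trauma". There is no symptom restriction.
- **Protocol 10.5.1:** "Formal definitions of the estimands are provided in the" Statistical Analysis Plan.
- **SAP 7.3.3, Estimand 6:** the aspirin minus LMWH difference in the probability of an observed DVT by 90 days, "where DVT will be categorized as (i) any, (ii) proximal, and (iii) distal".
- **SAP 7.3.3, Estimand 5 (non-fatal PE), for contrast:** "sub-classified as massive, sub-massive, clinically significant, clinically non-significant", besides an aggregate and a segmental split.

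Protocol 3.3.2 also gives the working rule behind the PE split. A PE outside the massive and submassive grades is clinically significant if the test was done because of symptoms or signs. It is clinically insignificant if found incidentally, on screening, or on a test done for another reason. No such rule is given for DVT.

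**The concern.** An imaging-confirmed clot in a patient without symptoms meets the protocol's definition of DVT and counts in SAP Estimand 6. It is not among the events that the protocol's reporting sentence names. An analyst who follows the SAP, as section 10.5.1 directs, will not produce the symptomatic estimate that section 3.3.2 promises. An analyst who follows section 3.3.2 will not produce Estimand 6. Until the texts agree, the choice of headline DVT figure is open and could be made after results by arm are known.

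The choice has substance. The trial is not blinded (protocol 10.2) and adds no clinical assessments of its own (6.2.2). Asymptomatic DVT is therefore found only when local practice leads to a scan, and a decision to scan can be influenced by knowing the arm. The protocol's background (2.1) also says that patients worry less about leg clots, which are often asymptomatic or of little clinical consequence, than about PE that might cause death or complications needing surgery. Estimand 6 puts those clots in the same count as symptomatic ones, with no line that separates them.

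**Working it through.** **1. Is there a figure to reproduce?** No. Version 11.0 and the SAP state no DVT rate, margin or power. The check is a comparison of texts followed by an illustration.

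**2. The texts side by side**

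| Feature | Protocol 3.3.2 | SAP Estimand 6 |
|---|---|---|
| Imaging confirmation | Required | Not stated |
| Symptom condition | Symptomatic events are those named for reporting | None |
| Location | Proximal, distal | Any, proximal, distal |
| Symptomatic/asymptomatic split | None | None |

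The symptomatic estimate appears in none of Estimands 1 to 9.

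**3. How far apart can the two readings be?** For each arm, let *s* be the probability of a symptomatic DVT and *a* the probability of having asymptomatic DVT only. With A for aspirin and L for LMWH:

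- symptomatic reading: RD = s_A − s_L
- all-DVT reading: RD = (s_A − s_L) + (a_A − a_L)

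The risk differences are equal when a_A = a_L. The estimates agree in every respect only if no asymptomatic DVT is found.

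**4. Illustration.** Inputs: 6,100 per arm (12,200 analysed, protocol 10.1), complete follow-up, and *assumed* rates s_L = 1.0% and s_A = 1.5%. The interval is RD ± 1.96 × √[p_A(1 − p_A)/n + p_L(1 − p_L)/n].

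For the symptomatic reading: √[(0.015 × 0.985 + 0.010 × 0.990)/6,100] = 0.00201, and 0.50 ± 1.96 × 0.201 gives 0.11 to 0.89 points.

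| a on LMWH / aspirin (assumed) | All DVT, LMWH / aspirin | RD, points (95% CI) | Risk ratio |
|---|---|---|---|
| 0 / 0 (symptomatic only) | 1.00% / 1.50% | 0.50 (0.11 to 0.89) | 1.50 |
| 0.25% / 0.25% | 1.25% / 1.75% | 0.50 (0.07 to 0.93) | 1.40 |
| 0.5% / 0.5% | 1.50% / 2.00% | 0.50 (0.03 to 0.97) | 1.33 |
| 1.0% / 1.0% | 2.00% / 2.50% | 0.50 (−0.03 to 1.03) | 1.25 |
| 0.5% / 0.25% | 1.50% / 1.75% | 0.25 (−0.20 to 0.70) | 1.17 |
| 0.5% / 0.75% | 1.50% / 2.25% | 0.75 (0.27 to 1.23) | 1.50 |

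Equal asymptomatic detection leaves the risk difference alone, widens the interval and dilutes the risk ratio. Unequal detection moves the risk difference by exactly a_A − a_L, in either direction.

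**The case against.** The best case against the point is that this is loose wording in one sentence rather than two settled definitions. Section 3.3.2 does not say that symptomatic events alone will be reported, and its preceding sentence fits Estimand 6. Specific Aim 2 is unrestricted, and section 10.5.1 gives the SAP precedence for estimands. In Estimand 6, the word *any* stands beside proximal and distal, so it most naturally means any location; the SAP never mentions asymptomatic DVT.

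Much of this stands. It means that the documents *can* give different results, not that they must. It does not remove the conflict: if the SAP governs, the protocol's reporting commitment goes unmet, and if the protocol's sentence governs, Estimand 6 is too broad.

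Three stronger readings are tempting, and the documents support none of them.

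- **That the SAP count would go against aspirin.** The background says "LMWH's are effective at limiting DVT, particularly asymptomatic DVT found on screening studies", but the sentence goes on to tie this to screening done for research. This trial adds no such screening, so the sentence does not show an LMWH effect on clots found in routine care.
- **That the mismatch could turn no difference into probable harm.** Rates can be chosen to suggest this. With symptomatic DVT 1.5% in both arms and asymptomatic DVT 0.5% on LMWH and 1.0% on aspirin, the difference moves from 0.0 (−0.43 to 0.43) to 0.5 (−0.03 to 1.03). This is one assumed scenario, and its interval includes zero.
- **That symptom status is not collected.** Appendix B lists no symptom item against DVT, but it is a schedule, not the forms. Imaging done for bleeding or VTE concerns is recorded. Whether those records show why a scan was done is unknown.

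It is also fair to note that the SAP's opening section lists DVT imaging among the information, masked to arm, that the study team could see. Imaging practice was therefore visible during the trial, but that does not settle which DVTs are counted. Nor would restricting the estimand to symptomatic DVT remove detection bias, since symptom reporting and scanning for symptoms are also open to influence in an unblinded trial.

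**Conclusion.** The point holds as a conflict between two current texts. Protocol 3.3.2 commits to reporting confirmed symptomatic DVT. SAP Estimand 6, the formal definition, has no symptom condition or split, and no other estimand supplies the symptomatic figure.

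The size and direction of any effect are unknown, because they depend on how many asymptomatic DVTs routine imaging finds in each arm. Under the assumed rates, the risk difference runs from 0.25 to 0.75 points against 0.50 for symptomatic DVT. These figures show the mechanism and are not a forecast. They rest on assumed rates, 6,100 per arm and complete follow-up.

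The consequence is limited. DVT is a secondary outcome, reported with a 95% confidence interval and no hypothesis test (protocol 10.5.1, SAP 7.4), so the non-inferiority conclusion on mortality is unaffected. The mismatch should still be corrected, because DVT is named in Specific Aim 2 and the correction is cheap.

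**What to change.** State one DVT definition, imaging confirmation included, in protocol 3.3.2 and SAP 7.3.3. Then set out Estimand 6 as three lines, each for any location, proximal and distal:

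1. symptomatic, imaging-confirmed DVT, as protocol 3.3.2 promises;
2. asymptomatic or incidental DVT;
3. all confirmed DVT, as the total.

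Classify each event, masked to arm, by the rule that section 3.3.2 already uses for PE: test done because of symptoms or signs, against screening, incidental finding or another reason. Say how a patient with both kinds is counted, for example on line 1 and once in the total. Settle this before anyone sees DVT results by arm.

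Restricting Estimand 6 to symptomatic DVT alone would also match the reporting sentence, but that is partly a preference. The three lines satisfy both texts and lose no information.

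**Cost.** Wording changes in both documents, plus some review of imaging or source records, since Appendix B lists no symptom item against DVT. The adjudication committee's role is described for deaths and PE but not for DVT, so this is added work for whoever does it. The symptomatic line will hold fewer events. In the illustration with 0.5% asymptomatic DVT in each arm, about 153 events are expected on it (0.010 × 6,100 + 0.015 × 6,100 = 152.5), against about 214 in the total (0.015 × 6,100 + 0.020 × 6,100 = 213.5).
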